SAP version history	2
·	
Table of contents	3
Introduction	4
Design overview	5
Sample size calculations	7
Analysis	10
Analysis	10
References	17

Introduction

This is an efficacy study statistical analysis plan for a two-armed parallel randomised controlled trial (RCT) evaluation of Salford Foundation's STEER programme. The efficacy study included an internal pilot trial started in January 2022 which concluded in May 2023. The trial moved to a full efficacy study in August 2023 and is due to complete in May 2025.

Salford Foundation's STEER programme (STEER) is a six-month intensive mentoring, coaching, family support and case management programme. It pairs young people who are at risk of serious youth violence and child criminal exploitation with a youth worker (mentor). Participants take part in STEER on a voluntary basis. The mentor delivers weekly face-to-face sessions which follow a toolkit of mandatory and optional themed interventions. In addition to these sessions, STEER provides weekly wrap-around case work and support for young people and offers their parents/carers a total of 14 hours of family support to facilitate greater family cohesion.

The key research question of the efficacy study is:

"Does a co-designed mentoring, coaching, family support, and case management programme delivered to children and young people with known family members or peers involved in offending behaviour, reduce the likelihood of participant involvement in serious youth violence and future offending or reoffending in comparison to receiving business as usual?"

The key primary outcome measure for the evaluation will be a reduction in prevalence of self-reported offending behaviours measured by the Self-Reported Delinquency Scale variety scale.²

Secondary outcomes include:

 A positive relationship between the young person and a significant adult (e.g., the mentor)

• Improved pro-social values and behaviours (measured by the Strengths and Difficulties Questionnaire (SDQ) pro-social values subscale).

² For more information see here: https://res.cloudinary.com/yef/images/v1623145465/cdn/19.-YEF-SRDS-guidance.pdf

- Improved emotional symptoms (measured by the SDQ emotional symptoms subscale).
- Improved behaviours (measured by the SDQ conduct problems subscale).
- Positive relationships/role models (measured by the SDQ peer relationships problems subscale).

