Data for all measures will be collected directly from participants using an online survey administered at baseline and approximately six-months post-randomisation.

Additional research questions include:

- 1. **Delivery**: Can the STEER programme work under ideal circumstances?
- 2. **Impact**: a) What is the impact of STEER? b) For whom does STEER work and under what conditions?
- 3. **Unintended consequences**: a) Does STEER have any unintentional consequences? If so, what are these? b) Do different groups of young people experience these differently?
- 4. **latrogenic effects**: Are there any serious negative effects attributed to STEER on any intended or unintended outcomes?
- 5. **Mechanisms**: a) How does STEER work to reduce children and young people's involvement in serious youth violence? b) Which factors contribute most to the observed outcomes?

Design overview

The efficacy trial is a two-arm, parallel randomised control trial (RCT). All young people referred into the project, who meet the eligibility criteria and who consent to be part of the evaluation will be allocated at random to a treatment or control group on a 1:1 basis.

The table below presents an overview of the efficacy study trial design.

Figure 1 Summary of Efficacy Study design

Trial design, including number of arms	Two-arm parallel randomised controlled trial with random allocation at the young person level	
Unit of randomisation	Individual participant	
Stratification variables	Not applicable	

(if applicable)				
Primary outcome	variable	Reduction in prevalence and variety of self-reported offending behaviours		
	measure (instrument, scale, source)	SRDS Variety Score		
	variable(s)	A positive relationship between the young person and a significant adult (e.g., the mentor) Improved pro-social values and behaviours		
		Improved emotional symptoms		
		Improved behaviours		
Secondary outcome(s)		Positive relationships/role models		
		A positive relationship between the young person and a significant adult (e.g., the mentor) measured by the Social Support and Rejection Scale (SSRS) (Roffman et al. 2000)		
	measure(s)	Improved pro-social values and behaviours measured by the pro-social behaviour sub-scale in the Strengths and Difficulties Questionnaire (SDQ) (Goodman, 2005)		
	(instrument, scale, source)	Improved emotional symptoms measured by the SDQ emotional symptoms sub-scale (Goodman, 2005)		

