	,	Improved behaviours measured by the SDQ conduct problems sub-scale (Goodman, 2005)		
		Positive relationships/role models measured by the Peer relationships problem sub-scale in the SDQ (Goodman, 2005)		
	variable	Reduction in prevalence and variety of self-reported offending behaviours		

Baseline for primary outcome	measure (instrument, scale, source)	SRDS Variety Score
	variable	Improved pro-social values and behaviours Improved emotional symptoms Improved behaviours Positive relationships/role models
Baseline for secondary outcome	measure (instrument, scale, source)	Improved pro-social values and behaviours measured by the Strengths and Difficulties Questionnaire (SDQ) prosocial values sub-scale (Goodman, 2005) Improved emotional symptoms measured by the SDQ emotional symptoms sub-scale (Goodman, 2005) Improved behaviours measured by the SDQ conduct problems sub-scale (Goodman, 2005) Positive relationships/role models measured by the measured by the SDQ peer relationships problem subscale (Goodman, 2005)

Sample size calculations

Originally, we determined the final required participant sample size a priori, conducting Power Calculations in line with YEF guidance which suggested a total sample of 654 young people (327 per group) over the pilot trial and efficacy study would allow a statistically significant result to be identified (Power=0.80, two tailed, P<.05) for a reduction of involvement in offending of 11%. We recognised that to account for attrition STEER would need to recruit a greater number of young people to reach a final sample size of 654 by the end of the evaluation.

Our original approach was conservative and in line with Lipsey and Wilson (2001) who state that ½ d=r, which is in turn equivalent to the difference in proportions. Figure 2 shows that if we suggest that 30% of the young people that STEER does not work with commit violence compared to 20.5% of the young people that STEER does work with committing violence (equivalent to a Cohen's d=.19) a total sample of 654 (327 in each group) would be needed to detect a statistically significant result (Power=.80), in a two-tailed test (p<.05). This level of Cohen's d was selected because it is conservative and is about equivalent to a 10-11%

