difference which is in line with a weighted average effect size of mentoring programmes, based on comparisons of 18 studies in a meta-analysis of mentoring and offending using a random effects model (d=.21, 95% confidence interval .07 to .34) presented by Jolliffe and Farrington, 2008.³

Figure 2 presents the results of our power analysis at the protocol stage. It shows that in line with our conservative approach; we used a pre-test/post-test correlation of 0. This is because at the time we had no reason to believe based on data collected during the pilot trial that the variance would be different between the treatment and control group. However, we knew that inclusion of a pre-test as a covariate in impact analyses helps to explain (error) variance in the post-test and improves the likelihood of uncovering programme impacts by reducing the standard error of the impact estimate. It was difficult to estimate what the pre-test/post-test correlation would be as this depended on unknown sample characteristics and the characteristics of the measure under investigation (the SRDS when used in a sample similar to STEER, i.e., those who are known to have peers or family members involved in offending behaviour). The greater the estimated pre-test/post-test correlation the lower the MDES and the smaller the sample needed to detect this. In practice however, if the pre-test/post-test correlation changes from 0.0 to 0.4 the MDES for a sample size of 500 decreases from .25 to .23.

In line with good practice, we have conducted power analysis based on our final sample once all randomisation has been completed. This power analysis is based on the numbers involved in the trial at baseline. This is also presented in Figure 2. As part of this calculation, we have included a pre- post-test correlation of 0.5. This is based on values obtained from unpublished data from an RCT using the same outcome measure and in a similar population of adolescents (Humayun et al., 2019) which we discovered after our original power analysis for the protocol. It is also based on treating the SRDS variety score as a continuous variable in analysis as opposed to a dichotomous variable.

Our power analysis shows an MDES of 0.186 based on baseline data

SPSS 25 was used for calculations for the original protocol. PowerUp! (Dong, N. and Maynard, R. A., 2013) has been used for the calculations once all randomisation and baseline data had been completed.

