³ Please note that this rapid evidence assessment found that mentoring was more effective in reducing reoffending when contact between mentor and mentee was greater, in smaller scale studies, and when mentoring was combined with other services and interventions.

Figure 2: Sample size calculations

		Protocol	Randomisation
Minimum Detectable Effect Size (MDES)		0.19	0.186
Pre-test/ post-test correlations	Level 1 (participant)	0.0	0.5
	Level 2 (cluster)	N/A	N/A
Alpha		0.05	0.05
Power		0.8	0.8
One-sided or two-sided?		Two-sided	Two-sided
Number of participants by end of the trial	Intervention	327	337
	Control	327	349
	Total	654	686

Recruitment and baseline data collection was completed in October 2024. The cumulative T1 sample at the end of this period was 686.

337 young people were allocated to the intervention group, and 349 to the control group. This is broadly in line with the intended 1:1 allocation ratio. More information can be seen in Figure 3 below.

Referred into STEER = 1052 Eligible for STEER = Disengaged/became 997 ineligible= 316* Consented = Withdrew/excluded 694 from evaluation = 8 Baseline measures = 686 STEER= Signposting 337 = 349

Figure 3: Consort flow diagram for baseline data collection

Analysis

Overview

The following presents the analytical approach for the Efficacy Study. We currently do not know the structure of the complete data-set (for example, extent of or categories of missing data etc.) that we will receive as part of the Efficacy Study. This should be considered when interpreting the following analytical plan.

There is considerable debate about best practice when it comes to the analysis of data from RCTs. For example, Twisk et al. (2018) advocate for utilising longitudinal analysis of covariance or a repeated measures analysis without the treatment variable, but with the interaction between treatment and time in the model controlled. They argue that failure to control for baseline differences in outcomes between the groups can lead to biased estimates in the treatment. Alternatively, others have cautioned against this approach (e.g., Sen, 2013).

Based on our understanding of the literature our analysis will be conducted using General Linear Models controlling for baseline measurement of the outcome variable. An intention to treat approach will be used with all models unless otherwise stated. This in line with YEF Guidance (YEF, 2021).

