A note on intra-cluster correlation

This is not a clustered randomised controlled trial. As such, we will not be calculating intraclass correlations.

Presentation of outcomes

The effect sizes will be calculated using Hedges' g, as specified in the following equation:

Hedges' $g = (x1 - x2) / \sqrt{(n1-1)*s12 + (n2-1)*s22} / (n1+n2-2)$

where:

x1, x2: The sample 1 mean and sample 2 mean, respectively

n1, n2: The sample 1 size and sample 2 size, respectively

s12, s22: The sample 1 variance and sample 2 variance, respectively

With a sample of greater than 20 there is limited difference with Cohen's d. However, if the standard deviations between the treatment and comparison group are different, we would

propose to use Glass' delta, which only uses the control group's standard deviation (Lipsey & Wilson, 2001).

The confidence interval for the Hedge's g statistic is:

 $g \pm \varphi - 1 (1-(\alpha/2))gse$

where:

 φ - 1 = the percent point function of the normal distribution

gse= the standard error of the g statistic

 $= V(n1+n2)/n1n2 + g^2/2(n1+n2)$

References

Dong, N. and Maynard, R. A. (2013). *PowerUp!*: A tool for calculating minimum detectable effect sizes and sample size requirements for experimental and quasi-experimental designs. *Journal of Research on Educational Effectiveness*, *6*(1), 24-67. doi: 10.1080/19345747.2012.673143

Goodman, R., 2005. *The Strengths and Difficulties Questionnaire*. Available at: https://www.sdqinfo.org/a0.html [Accessed 17/8/23].

Karcher, M.J. and Nakkula, M.J., 2010. Youth mentoring with a balanced focus, shared purposes, and collaborative interactions. *New Directions for Youth Development* 2010(126), pp.1-32.

Lipsey, M. and Wilson, D. (2021) Practical meta-analysis. Thousand Oaks, CA: Sage.

Roffman, J. G., Pagano, M. E., and Hirsch, B. J., 2000. *Social support and rejection scale*. Evanston, IL: Human Development and Social Policy, Northwestern University.

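### Individual randomisation does not justify ruling out intraclass correlation: STEER-arm participants probably share mentors, and neither the analysis nor the MDES allows for it

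*SAP*

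**What the plan says.** Figure 1 of the SAP (Design overview) describes a "Two-arm parallel randomised controlled trial with random allocation at the young person level". The section *A note on intra-cluster correlation* then says: "This is not a clustered randomised controlled trial. As such, we will not be calculating intraclass correlations". Figure 2 accordingly enters the cluster level as not applicable.

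The Introduction describes delivery. Of STEER it says: "It pairs young people who are at risk of serious youth violence and child criminal exploitation with a youth worker (mentor"). It adds: "The mentor delivers weekly face-to-face sessions which follow a toolkit of mandatory and optional themed interventions". Under *Further analyses*, the theory of change has the programme work through a better relationship with the mentor.

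The model in the *Analysis* overview contains the baseline outcome and a treatment indicator. *Primary outcome analysis* adds a repeated-measures form, an interaction term and a generalised-model alternative for a non-normal score. The SAP has no mentor term, cluster-robust standard error or mentor-level sensitivity analysis.

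On precision, *Sample size calculations* states: "Our power analysis shows an MDES of 0.186 based on baseline data".

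**The concern.** Random allocation of individuals makes the arms comparable at baseline. It does not make outcomes independent after baseline. If several STEER participants work with the same mentor, and mentors differ in the results they achieve, outcomes within a mentor's caseload are correlated. The control arm has no such structure. The variance of the STEER mean then has a between-mentor component that a model treating all 686 young people as independent leaves out, so the standard error of the treatment difference is too small for a conclusion about the programme in other mentors' hands.

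At stake are the coverage of the primary confidence interval, the 5% error rate and the stated MDES. There is little slack in the MDES, since 0.186 sits just below the protocol-stage figure of 0.19. And because the SAP declines to calculate an ICC, the final report could not show that mentor clustering was negligible, even if it was.

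**Working it through.** **Inputs from the SAP.** Error rates: "Power=0.80, two tailed, P<.05" (repeated for both columns of Figure 2). Arm sizes: "337 young people were allocated to the intervention group, and 349 to the control group". Covariate: "we have included a pre- post-test correlation of 0.5", so R² = 0.5² = 0.25.

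**Inputs the SAP does not give.** Number of mentors, young people per mentor (m) and within-mentor ICC. These are assumptions below. The ICC is that of the baseline-adjusted outcome. A mentor effect arises after randomisation, so adjusting for baseline shrinks the residual variance but not the mentor variance, and a given unadjusted ICC corresponds to a somewhat larger adjusted one.

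**Step 1: reproduce the stated MDES.** With N = 686, P = 337/686 and 683 degrees of freedom:

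MDES = (t₀.₉₇₅ + t₀.₈₀) × √[(1 − R²) / (P(1 − P)N)] = (1.963 + 0.842) × √(0.75 / 171.45) = 0.1856.

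This matches 0.186. The formula has no clustering in either arm, so the stated figure rests on that assumption.

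**Step 2: allow for mentors in the STEER arm only.** The variance of the treatment difference is inflated by

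V = {[1 + (m − 1)ICC]/337 + 1/349} / {1/337 + 1/349}.

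The standard error and the MDES are both multiplied by √V. The true two-sided type I error of the unadjusted-for-mentor test is approximately 2 × [1 − Φ(1.96/√V)].

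**Step 3: put numbers in.** Assume 15 mentors. Then 337/15 = 22.5, and m = 22 is used.

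| ICC | 1 + 21 × ICC | V | √V | MDES (0.186 × √V) | Type I error |
|---|---|---|---|---|---|
| 0 | 1.00 | 1.00 | 1.00 | 0.186 | 5.0% |
| 0.01 | 1.21 | 1.11 | 1.05 | 0.196 | 6.2% |
| 0.02 | 1.42 | 1.21 | 1.10 | 0.205 | 7.5% |
| 0.05 | 2.05 | 1.53 | 1.24 | 0.230 | 11.4% |

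Simulation with random mentor effects (40,000 runs per cell, two-sample test without baseline adjustment) agrees: 6.1% to 6.4%, 7.6% and 11.4%.

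**Step 4: vary the number of mentors.** Over ICC 0.01 to 0.05, simulated type I error runs from 7.2% to 14.6% with 10 mentors and from 5.7% to 8.0% with 30. At the mild end (ICC 0.01 and 5 to 20 young people per mentor), the standard error should be only 1% to 5% larger and the MDES is 0.187 to 0.194.

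**Step 5: change the target of inference.** If the 15 mentors are treated as fixed, with effects averaging zero, simulated type I error is 5.1%, 4.9% and 4.7% at the three ICCs. The inflation in Step 3 therefore belongs to inference beyond these mentors.

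**The case against.** Four points can be made for the SAP.

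*Nothing in the document shows that the standard errors are wrong.* A reader might infer that they are too small as a matter of fact. The SAP does not support that: it gives no ICC and no caseload, and it does not say that each mentor serves several young people. Shared mentors are a strong inference from 337 allocations to a six-month programme, but still an inference. A positive ICC is an assumption. This objection stands, and the point is worded conditionally for that reason.

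*The theory of change does not name mentor skill.* It names the relationship with the mentor. Relationship quality may vary mainly among young people with the same mentor, which would produce little clustering, and a common toolkit works in the same direction. This also stands. The text makes a mentor effect plausible but does not establish one.

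*Inference could be confined to these mentors.* An efficacy trial that asks whether a programme can work under ideal circumstances might reasonably do so, and Step 5 shows the ordinary standard error would then serve. But the SAP states no such restriction, and its main research question is about the programme.

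*A new primary model would be hard to defend.* With perhaps 10 to 15 mentors, a small ICC is poorly estimated. The SAP may also move to a generalised model, which a Gaussian mixed model does not cover. That argues for a sensitivity analysis rather than a change of primary analysis, and the recommendation follows it.

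**Conclusion.** The reasoning in the intra-cluster note is faulty: individual allocation is not a reason to leave the ICC uncalculated when one arm is delivered by mentors. That conclusion needs no assumption.

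The numerical consequence is conditional on three things: mentors each serve several young people, the mentor ICC is above zero, and inference is meant to reach beyond the mentors in the trial. Under those conditions the planned standard error of the treatment difference (not only that of the STEER mean) is too small. With 15 mentors, it should be about 5%, 10% or 24% larger at ICCs of 0.01, 0.02 and 0.05. The effect could be small, and the SAP as written would leave that unknown.

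The SAP should be changed on this point. The documents do not show that the primary analysis is invalid.

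**What to change.** In *A note on intra-cluster correlation*, keep the statement that the trial is not cluster-randomised and replace the conclusion drawn from it with these commitments:

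- Link mentor ID from delivery records for STEER-arm participants.
- Report the number of mentors, their caseloads and the STEER-arm mentor ICC with its confidence interval.
- Pre-specify a sensitivity analysis of the primary outcome: a partially nested mixed model with a random mentor effect in the STEER arm only, arm-specific residual variance and small-sample degrees of freedom. If the generalised branch is used for the primary analysis, use its generalised mixed equivalent.
- To keep intention to treat, treat STEER-arm participants who never started with a mentor as clusters of one, and assign those who changed mentor to their first mentor.

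In *Sample size calculations*, state that 0.186 assumes no mentor clustering, and show the MDES over a range of ICCs using the actual caseloads.

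The cost is one linked variable and one extra model. The sensitivity confidence interval may be wider, and the ICC will be imprecise if mentors are few. The SAP says the analysis syntax will be developed once all data have been collected, so the addition need not mean reworking code.

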[•] These are young people who disengaged or became ineligible because they: refused the service, had a parent who refused the service, moved out of area, were uncontactable, had too many services involved, or were deemed too complex due to an escalation in risk following the acceptance of referral.

The primary outcome for the evaluation of STEER is a reduction in prevalence of self-reported offending behaviours between baseline and six months as measured by the SRDS variety score.

The secondary outcomes that we are investigating are that young people receiving STEER compared to the business as usual (control) group have (See Figure 1 for more information about measures):

- A positive relationship with their mentor.
- Improved pro-social values and behaviours.
- Improved emotional symptoms.
- Improved behaviours
- Positive relationships/role models.

The General Linear Model will include the appropriate baseline outcome measure and the treatment dummy variable. For example, for the analysis of the primary outcome measure (SRDS Variety Score) the baseline SRDS variety score measure will be included and whether the individual received STEER or not

The purpose of these analyses is to estimate the difference between the STEER arm and the business-as-usual arm for each of the primary and secondary outcomes.

Variable transformation

It is possible that the baseline and outcome variables may be skewed. Skew will be assessed using the traditional criteria based on their distribution (i.e., skews of greater or equal to 1.0 or less than or equal to -1.0). Arguably, it is more desirable to use a generalised liner model (GLM) for the appropriate modelling of non-normally distributed variables (e.g., Akram et al., 2023), than it is to transform the data.

The analytic approach has been developed a priori and will be conducted with SPSS.

The syntax for all analysis will be provided once it has been developed after all data has been collected.

Primary outcome analysis

The primary outcome is a reduction in offending measured by the SRDS Variety Score. All young people will have completed the SRDS questionnaire before randomisation and again at around six months post-randomisation.

The SRDS Variety Score is measured on a scale from 0-19 with 0 indicating the young person has not reported any of the 19 forms of delinquency/offending behaviour and a score of 19 indicating that they have undertaken all forms of delinquency/offending behaviour.

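### The reported effect size (Hedges' g) and its interval are unadjusted, so they do not express the baseline-adjusted primary analysis and can disagree with its test

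*SAP*

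**What the plan says.** **Analysis model.** The SAP's Analysis, Overview states that "our analysis will be conducted using General Linear Models controlling for baseline measurement of the outcome variable", and then: "The General Linear Model will include the appropriate baseline outcome measure and the treatment dummy variable". The Primary outcome analysis section describes the model differently, as a repeated-measures general linear model, or a generalized linear model if the score is not normal, with an interaction term. Both descriptions use the baseline score.

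**Power.** Sample size calculations explains that the pre-test covariate is there to lower the standard error of the impact estimate. It gives an MDES of 0.186 for 337 and 349 participants at a pre/post correlation of 0.5.

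**Reporting.** Presentation of outcomes begins "The effect sizes will be calculated using Hedges"' g. Its numerator is defined by "x1, x2: The sample 1 mean and sample 2 mean, respectively" and its denominator by "s12, s22: The sample 1 variance and sample 2 variance, respectively". The interval uses "gse= the standard error of the g statistic", which is the square root of (n1+n2)/(n1·n2) + g²/(2(n1+n2)). Glass' delta replaces g "if the standard deviations between the treatment and comparison group are different". The section does not mention the model estimate, adjusted means or the model's standard error.

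**The concern.** The plan adjusts for baseline to gain precision and counts that gain in its MDES, but its only defined effect size and interval make no use of baseline. Three consequences follow.

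- The reported g and the model's estimate differ by chance baseline imbalance.
- The reported interval does not show the precision the trial was powered on.
- The final report could show a significant primary test beside an effect-size interval that includes zero, or the reverse, and the SAP gives no rule for which result carries the conclusion.

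The Glass' delta switch adds a choice made after seeing the data. Two sample SDs always differ to some extent, so without a threshold the condition is always open to being met. The SAP gives no interval to accompany delta.

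**Working it through.** **Inputs from the SAP.** n1 = 337, n2 = 349, two-sided alpha 0.05, power 0.80, r = 0.5, MDES 0.186. **Assumptions.** No attrition (the SAP gives no figure), normal scores with SD 1, and r varied from 0.3 to 0.7.

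**1. Reproduce the MDES.** Let k = 1/337 + 1/349, so √k = 0.0764. The multiplier t(0.975) + t(0.80) on 683 df is 2.806.
- r = 0.5: 2.806 × √0.75 × 0.0764 = 0.1856, which rounds to the stated 0.186.
- r = 0: 2.806 × 0.0764 = 0.214.

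The stated figure is therefore a baseline-adjusted one.

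**2. Standard errors under the Overview model (baseline plus treatment).**
- SAP formula at g = 0.14: √(686/(337 × 349) + 0.14²/(2 × 686)) = 0.0765.
- Adjusted model: √(0.75 × k) = 0.0661.
- Ratio: 0.0765/0.0661 = 1.157. At g near 0 it is 1/√0.75 = 1.155.

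Equal proportional loss in the two arms widens both and leaves the ratio essentially unchanged.

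**3. What this does to a result.** Suppose both methods gave the same point estimate. The model is significant above 1.96 × 0.0661 = 0.130, while the SAP interval excludes zero only above about 0.150. At 0.14 the model gives p = 0.034 and an interval of 0.01 to 0.27. The SAP interval is −0.01 to 0.29.

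**4. Point estimates do not in fact coincide.** The adjusted difference and raw g differ by r times the chance baseline imbalance. The SD of that difference is 0.5 × 0.0764 = 0.038 at r = 0.5 (0.023 at r = 0.3, 0.053 at r = 0.7).

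**5. Simulated agreement of verdicts.** Baseline-adjusted model against the SAP's interval for g, true effect 0.186, 5,000 trials per setting:

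| r | Model significant | g interval excludes 0 | Verdicts differ |
|---|---|---|---|
| 0.3 | 72.2% | 68.1% | 9.4% |
| 0.5 | 79.8% | 67.8% | 17.3% |
| 0.7 | 93.0% | 69.5% | 25.6% |

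At r = 0.5, 14.6% of trials had a significant model with a g interval including zero, and about 2.6% the reverse.

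**6. The other model description.** If the repeated-measures model is read as a group-by-time change contrast, its standard error is √(2(1 − r)k).
- r = 0.5: √(1.0 × k) = 0.0764, the same as the SAP formula at g near 0.
- r = 0.3: √(1.4 × k) = 0.0904, larger than the SAP formula.

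The change estimate differs from the follow-up difference by the whole baseline imbalance (SD 0.076), and at r = 0.5 the verdicts differ in about 30% of trials.

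**7. Glass' delta.** As an illustration, take a STEER SD 15% below the control SD. The pooled SD is √((336 × 0.85² + 348 × 1)/684) = 0.929 of the control SD. So g is 1/0.929 = 1.08 times delta, about 8% larger from the same data.

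**The case against.** The strongest reply is that nothing here is invalid. Unadjusted g is a standard descriptive measure. Under randomisation it targets the same difference as the adjusted model, and when x1 and x2 are raw follow-up means its interval has its nominal coverage (about 95% in simulation). The Overview also says the models will estimate the difference between arms, so a model estimate will exist, and the primary test and its type I error are untouched. All of that stands. What remains is that the SAP does not tie its reported effect size to that estimate.

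Some stronger readings are tempting but not supported:

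- **That the g interval is simply too wide.** This holds only if adjusted means are put in for x1 and x2. The section says neither raw nor adjusted and names no time point; unadjusted follow-up means is the plain reading, not a stated fact.
- **That the 16% gap holds whatever model is used.** It belongs to the Overview model at r = 0.5. Under a change contrast it disappears at r = 0.5 and reverses at r = 0.3.
- **That the trial's power is 68% rather than 80%.** The SAP does not make the g interval the decision rule, nor does it call g the headline result.
- **That the g interval formula is to be used for Glass' delta.** The SAP labels that formula for Hedges' g only. The fair point is that delta has no interval at all.
- **That the printed equation for g is algebraically wrong.** The bracketing is probably an effect of PDF text extraction, since other symbols in the section are also garbled. Nothing here rests on it.

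**Conclusion.** The point holds as a mismatch between the analysis and its reporting. The SAP's only defined effect size and interval are unadjusted, while the analysis and the MDES are baseline-adjusted. Under the Overview model with 337 and 349 participants, r = 0.5 and no attrition, this costs about 16% in standard error and produces conflicting verdicts in about 17% of trials at the MDES, with a range of about 9% to 26% for r from 0.3 to 0.7. Under the change-contrast reading there is no loss of precision at r = 0.5, but the conflict rises to about 30%. So the size depends on which model description applies, while the mismatch arises under both. If a generalized linear model is used, its effect may be on another scale, and the SAP gives no route from that to g. The undefined trigger for Glass' delta is a separate, smaller fault in the same section.

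**What to change.** Amend Presentation of outcomes before the arms are compared:

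1. Define the effect size as the baseline-adjusted mean difference from the primary model divided by the pooled unadjusted six-month SD. Take the 95% interval as the model's limits divided by the same SD.
2. If a generalized linear model is used, report the effect and interval on the model's own scale. Derive the standardised difference from the model's adjusted (marginal) mean difference on the score scale, with a delta-method or bootstrap interval.
3. Keep unadjusted g, if wanted, only as a labelled descriptive figure.
4. Remove the conditional switch to Glass' delta, or report delta for every outcome with its own interval.

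The cost is SAP wording and a few lines of syntax, which the SAP says will be developed only after data collection. No extra data are needed.
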